1. PROTOCOL SYNOPSIS FOR STUDY RES117169

Rationale

GSK3128349: GSK3128349 is a human domain antibody (dAb) that binds noncovalently to serum albumin with high affinity (also referred to as an 'AlbudAbTM'). It contains a cysteine residue engineered at the C terminus of the molecule that can be used for the covalent attachment of a pharmacologically active entity As such, GSK3128349 is a scaffold that has of itself no pharmacological action, but has the potential to be conjugated with a pharmacologically active entity [O'Connor-Semmes, 2014].

GSK3128349 is a platform to extend half-life and alter biodistribution of therapeutics: Typically, dAbs are small (~15 kDa) and therefore are excreted renally in a matter of hours. Due to the combination of the high affinity of GSK3128349 for albumin and the high concentrations of albumin, it is expected that GSK3128349 will be bound to albumin the majority of the time. Therefore, AlbudAbs, like GSK3128349, form a complex too big to be subject to renal clearance. Furthermore, the binding of GSK3128349 to albumin confers some of the pharmacokinetic and biodistribution properties of albumin to GSK3128349; and hence any pharmacologically active entity conjugated to it. This includes AlbudAbs bound to albumin being subject to Neonatal Fc Receptor (FcRn) dependent albumin recycling enhancing the exposure half-life. As a result of these effects AlbudAbs can persist in the body for several days or even weeks. We expect the half life of GSK3128349 in humans to approach that of albumin (~19 days [Peters, 1985] [Peters, 1996(a)]). Therefore, GSK3128349 has the potential to significantly enhance the medicinal value of therapeutics conjugated to GSK3128349 by increasing their half-life and/or modulating their biodistribution [Kratz, 2008].

Study Objective: This study will determine the biodistribution and pharmacokinetics of the AlbudAb scaffold GSK3128349. The data will inform and validate a Physiologically Based Pharmacokinetics (PBPK) model, which will predict the distribution of future therapeutics conjugated to GSK3128349, as well as other AlbudAbs.

The validated PBPK modeling will improve our future clinical study designs by providing more accurate estimates of tissue exposures, which will lead to better: dose selection, timing of biomarker measurements, target engagement, and ultimately efficacy. This could potentially lead to a reduced number of assessments and/or subjects enrolled in future clinical trials. Furthermore, the PBPK modeling will be applied pre-clinically, yielding better selection of targets for discovery programs, and informing affinity requirements for discovery lead optimization efforts.

The data generated through this study will benefit all ongoing and future AlbudAb programs, and will provide generally applicable information to support understanding of biodistribution processes for all protein-based therapies.

Objective(s)/Endpoint(s)

[figure not shown]
	PRIMARY OBJECTIVE	END POINTS
1.1	Evaluate biodistribution of ⁸⁹ Zr-GSK3128349 in regions of interest following IV administration to support future AlbudAb products and the development of a PBPK model.	 Quantitative parameters (including but not limited to ⁸⁹Zr-GSK3128349 concentration) derived from Positron Emission Tomography – Computed Tomography (PET-CT) data (e.g. Standardised Uptake Values (SUVs)^a, volume of Regions of Interest (ROI) to assess average and total uptake into regions of interest (e.g. liver, kidney, muscle, spleen, heart, lung, bladder, thymus – if feasible -, blood and bone).
	SECONDARY OBJECTIVES	END POINTS
2.1	Measure PK of ⁸⁹ Zr- GSK3128349 by whole blood, plasma and urine radiolabel detection to support future AlbudAb products and the development of a PBPK model.	• Whole blood, plasma and urine radioactivity concentrations and derived pharmacokinetic parameters, as data allows, based on blood, plasma and urine scintillation counting.
2.2	Measure PK of GSK8128349 by mass spectroscopy to support the development of a PBPK model.	 Plasma concentrations and derived pharmacokinetic parameters. Compare plasma exposure assessments via different GSK3128349 mass spectroscopy methods.
2.3	Measure dosimetry of ⁸⁹ Zr- GSK3128349 from PET scans and blood radioactivity.	Organ doses (mSv)Effective dose (mSv)
2.4	Assess the safety and tolerability of ⁸⁹ Zr-GSK3128349.	 Adverse events (AEs), serious adverse events (SAEs). Safety laboratory values, proteinuria, electrocardiograms (ECGs) and vital signs.
2.5	Investigate the presence and levels of anti-GSK3128349 antibodies, including pre- and post-dose.	Incidence of anti-GSK3128349 antibodies.Serum titres of anti-GSK3128349 antibodies.
a SU	V_{mean} for larger ROI (\geq 3 cm), SUV _{pe}	_{ak} for smaller ROI.

Overall Design

This open label single centre study will investigate the biodistribution and pharmacokinetics of the AlbudAb platform scaffold protein GSK3128349. Hence, GSK3128349 will be administered as a single drug product consisting of a mix of

unlabeled GSK3128349 and ⁸⁹Zr-GSK3128349 (GSK3128349 radiolabelled with zirconium).

Study Schematic

Study Overview

- On Day 1, enrolled subjects will receive one intravenous (IV) infusion of ⁸⁹Zr-GSK3128349 to deliver a dose of 1 mg and undergo PET/CT scans and blood sampling assessments prior to discharge at 24 hrs post-dose, on day 2.
- Subjects will be required to visit the clinic repeatedly over the subsequent 42 days and undergo further blood sampling and PET/CT scans up to 10-12 days after dosing. This will monitor ⁸⁹Zr-GSK3128349 concentrations in various regions of interest (ROI) over time.
- Blood samples will be taken for radioactivity, pharmacokinetic, immunogenicity, and safety assessments (
- After completion of the first 2 subjects, dosimetry assessments will be performed and used to refine the radiation dose administered to subsequent subjects.
- Urine will be collected during the first 24 hours and measured with respect to radioactivity and drug.
- The expected total duration of a subject's participation is approximately 10 weeks, including the screening period of up to 28 days.

Type and Number of Subjects

A single cohort of six to eight healthy male subjects will be enrolled into the study.

Analysis

Interim Analysis

There are no formal interim analyses planned. However, the following in-stream data review is planned:

Following completion of the first two subjects' PET scans, the study team will evaluate the emerging PET-CT scan data for:

- Dosimetry to potentially refine the radiation dose estimates, and to identify other ROI for further investigation, if required.
- Determine scan time points post dose of subsequent subjects.

Primary Analyses

The following analysis is planned for primary endpoints:

Analysis	Details
Endpoints	• Quantitative parameters (including but not limited to ⁸⁹ Zr-GSK3128349 concentration) derived from PET-CT data (e.g. Standardised Uptake Values (SUVs) ^a , volume of ROI) to assess average and total uptake into regions of interest (e.g. liver, kidney, muscle, spleen, heart, lung, bladder, thymus – if feasible -, blood and bone
Endpoint Definitions	• SUV: A simple way of determining activity in PET imaging for each region of interest, which is mathematically derived ratio of tissue radioactivity concentration at a point in time C(T) and the injected dose of radioactivity per kilogram of the patient's body weight:
	SUV = C(T)/[injection dose (MBq)/patient's weight (kg)]
	• Volume: The volume of specified organ as measured in PET or CT images.
Analysis (Raw Data)	• Descriptive statistics where appropriate, (i.e. n, arithmetic mean, geometric mean, standard deviation, minimum, median and maximum) will be calculated for all generated PET-CT imaging endpoints over time.
	• Graphical displays will be produced over time for applicable PET-CT imaging endpoints.
	• If analysed, all data will be listed.
Statistical Analysis (Modelled)	• If data permits, further statistical analyses (i.e. mixed effects models) will be performed to estimate quantitative parameters in ROI over time from PET-CT following IV administration.
	• Full details will be specified in the RAP.
a SUV _{mean}	for larger ROI (\geq 3 cm), SUV _{peak} for smaller ROI

Secondary Analyses

• Pharmacokinetics (Concentration Data & Derived Parameters)

РК	Details	
Concentration	• Whole blood, plasma and urine concentrations of ⁸⁹ Zr-GSK3128349 and plasma concentrations of GSK2138349 data will be graphically represented, descriptively summarised and listed appropriately.	
Parameters	 Whole blood and plasma concentrations time data of ⁸⁹Zr-GSK3128349 and plasma concentrations time data of GSK3128349 will be analyzed by non-compartmental methods. Calculations will be based on the nominal sampling times recorded during the study. As data permits, from the plasma concentration-time data, the following PK parameters may be determined: Maximum observed plasma concentration (Cmax) Time to Cmax (Tmax) Apparent terminal phase half-life (t1/2). Area under the curve: AUC[0-t] for ⁸⁹Zr-GSK3128349 and GSK3128349, AUC[0-∞] only for GSK3128349 Clearance Volume of distribution Additional PK parameters may be included as required. Pharmacokinetic data will be presented in graphical and/or tabular form, summarized descriptively and listed. 	

• Dosimetry

Dosimetry results as organ radiation doses and subject effective dose will be listed.

• Safety, Tolerability & Immunogenicity

Safety, tolerability and immunogenicity data will be presented in tabular and/or graphical format and summarized descriptively according to GSK's Integrated Data Standards Library (IDSL) standards.

[figure not shown]
2. INTRODUCTION

2.1. Brief background

Albumin is the most prevalent protein in human plasma (35-54 g/L) and has a half-life in humans of approximately 19 days [Peters, 1985] [Peters, 1996(a)]. Total extravascular albumin is about twice that of the intravascular pool, and exchange occurs between these pools at a rate of 4-5% total albumin/hour [Peters, 1996(b)]. However, this is a simplification of a complex process. Certain organs (e.g. lungs, liver, kidney) show rapid exchange with intravascular albumin, and others (e.g. skin, muscle), that account for a large amount of extravascular albumin due to their size, show a much slower exchange [Peters, 1996(b)].

GSK3128349 is a human domain antibody (dAb) that binds non-covalently to serum albumin with high affinity (also referred to as an 'AlbudAb'). It contains a cysteine residue engineered at the C terminus of the molecule that can be used for the covalent attachment of a pharmacologically active entity (Figure 1). As such, GSK3128349 is a scaffold that has of itself no pharmacological action, but has the potential to be conjugated with a pharmacologically active entity [O'Connor-Semmes, 2014]. [The Cterminal cysteine of GSK3128349 used in the current study is blocked with N-ethylmaleimide in order to avoid undesirable chemical reactivity towards serum proteins or covalent dimerization.]

Figure 1 Schematic of GSK3128349 AlbudAb, depicted binding to albumin (HSA) and with a conjugated therapeutic drug.

Typically, dAbs are small (~15 kDa) and therefore are excreted renally in a matter of hours. Due to the combination of the high affinity of GSK3128349 for albumin and the high concentrations of albumin, it is expected that GSK3128349 will be bound to albumin the majority of the time. Therefore, AlbudAbs, like GSK3128349, form a complex too big to be subject to renal clearance. Furthermore, the binding of

GSK3128349 to albumin confers some of the pharmacokinetic and biodistribution properties of albumin to GSK3128349; and hence any pharmacologically active entity conjugated to it. This includes AlbudAbs bound to albumin being subject to Neonatal Fc Receptor (FcRn) dependent albumin recycling enhancing the exposure half-life. As a result of these effects AlbudAbs can persist in the body for several days or even weeks. We expect the half life of GSK3128349 in humans to approach that of albumin (~19 days [Peters, 1985] [Peters, 1996(a)]). The medicinal value of therapeutics conjugated to GSK3128349 has the potential to be significantly enhanced by increasing their half-life and/or modulating their biodistribution [Kratz, 2008].

2.2. Study rationale

The study will determine the biodistribution and pharmacokinetics of the AlbudAb scaffold (GSK3128349). The data will inform and validate a Physiologically Based Pharmacokinetics (PBPK) model, which will predict the distribution of future therapeutics conjugated to GSK3128349, as well as other AlbudAbs.

The validated PBPK modeling will improve our future clinical study designs by providing more accurate estimates of tissue exposures, which will lead to better: dose selection, timing of biomarker measurements, target engagement, and ultimately efficacy. This could potentially lead to a reduced number of assessments and/or subjects enrolled in future clinical trials. Furthermore, the PBPK modeling will be applied pre-clinically yielding better selection of targets for discovery programs, and informing affinity requirements for discovery lead optimization efforts.

The data generated through this study will benefit all ongoing and future AlbudAb programs, and will provide generally applicable information to support understanding of biodistribution processes for all protein-based therapies.

3. OBJECTIVE(S) AND ENDPOINT(S)

	PRIMARY OBJECTIVE	END POINTS
1.1	Evaluate biodistribution of ⁸⁹ Zr-GSK3128349 in regions of interest following IV administration to support future AlbudAb products and the development of a PBPK model.	 Quantitative parameters (including but not limited to ⁸⁹Zr-GSK3128349 concentration) derived from Positron Emission Tomography – Computer Tomography (PET-CT) data (e.g. Standardised Uptake Values (SUVs)^a, volume of Regions Of Interest (ROI) to assess average and total uptake into regions of interest (e.g. liver, kidney, muscle, spleen, heart, lung, bladder, thymus – if feasible -, blood and bone).

	SECONDARY OBJECTIVES	END POINTS
2.1	Measure PK of ⁸⁹ Zr- GSK3128349 by whole blood, plasma and urine radiolabel detection to support future AlbudAb products and the development of a PBPK model.	• Whole blood, plasma and urine radioactivity concentrations and derived pharmacokinetic parameters, as data allows, based on blood, plasma and urine scintillation counting.
2.2	Measure PK of GSK8128349 by mass spectroscopy (MS) to support the development of a PBPK model.	 Plasma concentrations and derived pharmacokinetic parameters. Compare plasma exposure assessments via different GSK3128349 mass spectroscopy methods.
2.3	Measure dosimetry of ⁸⁹ Zr- GSK3128349 from PET scans and blood radioactivity.	Organ doses (mSv)Effective dose (mSv)
2.4	Assess the safety and tolerability of ⁸⁹ Zr-GSK3128349.	 Adverse events (AEs), serious adverse events (SAEs). Safety laboratory values, proteinuria, electrocardiograms (ECGs) and vital signs.
2.5	Investigate the presence and levels of anti-GSK3128349 antibodies, including pre- and post-dose.	 Incidence of anti-GSK3128349 antibodies. Serum titres of anti-GSK3128349 antibodies.
a SU	V_{mean} for larger ROI (\geq 3 cm), SUV _{pe}	_{ak} for smaller ROI.

4. STUDY DESIGN

4.1. Overall Design

Using a single cohort of six to eight healthy male subjects, this open label single centre study will investigate the biodistribution and pharmacokinetics of the AlbudAb platform scaffold protein GSK3128349. Hence, GSK3128349 will be administered as a single drug product consisting of a mix of unlabeled GSK3128349 and ⁸⁹Zr-GSK3128349 (GSK3128349 radiolabelled with zirconium, see Section 6).

PET scanning, using ⁸⁹Zr labelling, is most optimal among available radioisotopes for monitoring longer half life therapies, such as antibodies, and is both quantitative and capable of assessing sites throughout the body, including within organs such as the kidneys and liver [Vugts, 2013]. This strategy has previously been used to monitor the distribution of the anti-HER2 antibody, Trastuzumab, among others [Dijkers, 2010]. Specifically, we have radiolabeled GSK3128349 with ⁸⁹Zr and have demonstrated that the rat radio-PK of ⁸⁹Zr-GSK3128349 is strikingly similar to the Pharmacokinetics (PK) of unlabeled GSK3128349, providing supportive data that the ⁸⁹Zr labelling of

GSK3128349 does not impact its functionality. Likewise, no difference in the albumin binding of ⁸⁹Zr-GSK3128349 was detected using an *in vitro* assay. Since the half-life of the radionuclide zirconium (⁸⁹Zr) is 3.3 days, labelling GSK3128349 with ⁸⁹Zr allows imaging to take place over a maximal time frame of up to about 10-12 days. This 10-12 day time frame encompasses the expected biodistribution phase and will allow gathering of biodistribution information for GSK3128349 via PET scanning and radio PK. The biodistribution is key information required to enhance our PBPK modelling ability. As ⁸⁹Zr signal will be limited during the elimination phase (beyond 12 days) and the anticipated half-life will approach that of albumin (approximately 19 days), measurement of plasma PK will be utilized to help inform upon GSK3128349 elimination.

[figure not shown]

Figure 2 Study Schematic

[figure not shown]
NOTE: Please refer to time and events table for PET and PK blood sampling timings

Study Overview

- On Day 1, enrolled subjects will receive one intravenous (IV) infusion of ⁸⁹Zr-GSK3128349 to deliver a dose of 1 mg (for further detail on dose see Section 4.3), and undergo PET/CT scans and blood sampling assessments prior to discharge at 24 hrs post-dose, on day 2.
- Subjects will be required to visit the clinic repeatedly over the subsequent 42 days and undergo further blood sampling and PET/CT scans up to 10 days after dosing. This will monitor ⁸⁹Zr-GSK3128349 concentrations in various regions of interest (ROI) over time.
- Blood samples will be taken for radioactivity, pharmacokinetic, immunogenicity, and safety assessments (see Time and Events table, Section 7.1.2).

- After completion of the first 2 subjects, dosimetry assessments will be performed and used to refine the radiation dose administered to subsequent subjects. This will ensure the total radiation exposure in subsequent subjects is kept below approximately 10 mSv. The data obtained with the first 2 subjects may also be used to adjust the time post dose for PET scans performed on subsequent subjects.
- Urine will be collected during the first 24 hours and measured with respect to radioactivity and drug.
- The expected total duration of a subject's participation is approximately 10 weeks, including the screening period of up to 28 days.

4.1.1. PET/CT Image Acquisition Workflow

4.1.2. PET scans

- Details of the procedures for the acquisition of PET scans and co-localisation low dose CT scans will be included in the Image Acquisition Guidelines. Each PET scan will have a typical duration of up to 60 minutes.
- PET scan data from the first two subjects will be analysed and used for a potential refinement of the radiation dose estimates and post dose scan time points for subsequent subjects.
- Radioactivity measurements from blood will also be used for dosimetry calculations in first 2 subjects (see Section 7.1 Time & Events Table).

Subject	Scan Times
1 st Subject	Following completion of the IV infusion the subject will be scanned at the following times:
	$1 \text{ hr} \pm 30 \text{ min}$
	$6 \text{ hrs} \pm 1 \text{ hr}$
	$24 \text{ hrs} \pm 1 \text{ hr} (\text{Day } 2)$
	5 days (Day 6)
2 nd Subject	Following completion of the IV infusion the subject will be scanned at the following times:
	$3 hrs \pm 30 min8 hrs \pm 1 hr$
	3 days (Day 4)
	5 days (Day 6)
Remaining Subjects	Four to six additional subjects will undergo scanning, utilising modified scan timings such that the biodistribution is fully profiled over the time period of up to 10-12 days post dosing. A maximum of 4 PET/CT scans will be undergone by each subject.

Table 1PET scanning times

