6. STUDY TREATMENT

The term 'study treatment' or ⁽⁸⁹Zr-GSK3128349' is used throughout the protocol to describe the drug product, which is a mix of ⁸⁹Zr labeled and unlabelled GSK3128349 received by the subjects as per the protocol design. Details of ⁸⁹Zr labelled GSK3128349 can be found in the relevant non Investigational Medicinal Product (IMP) document.

Product name:	⁸⁹ Zr-GSK3128349						
Formulation	50 mM sodium acetate buffer and 200 mM sucrose at pH						
Description:	5.20-5.80, associated with about 15 MBq of radioactivity.						
Dosage Form:	Solution for IV administration						
Unit Dose	Approximately 10 mL of 0.1mg/mL ⁸⁹ Zr-GSK312834						
Strength							
Dose level	1 mg						
Route/	IV as a continuous infusion over 20 mins						
Administration/							
Duration:							
Dosing	Single dose						
Instructions:							
Physical	Liquid in 50mL vial						
Description:							
Manufacturer/	VUMC, Amsterdam						
Source of							
procurement:							

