7.1.2. Scanning & Dosing

Day of study	Day - 1			D	ay 1				Day 6	Day 13 ± 1 day	Day 20 ± 2 days	Day 31 ± 2 days	
Time post dosing		Pre-dose	0	1 hour	3 hours	6 hours	8 hours	24 hours					
Admission to Unit	Х												
Brief Physical Exam	Х							Xa					
Medical/Medication/Drug/Alcohol Hx	Х												
12-lead ECG		Xf		Х				Х					
Vital Signs		Х		Х				Х					
Urine Drug/Alcohol	Х												
Urinalysis	Х							Xi		Х	Х	Х	
Spot Urine Protein/Creatinine ratio	Х							Xe			Х		
Haematology								Х				Х	
Clinical chemistry	Х							Х		Х	Х	Х	Х
Randomisation	Х												
Immunogenicity Blood Sample		Х											
IV Infusion Dosing			Х										
PET imaging and co-localising CT (first subject) ^a				x		х		Х		Х			
PET imaging and co-localising CT (second subject) ^a					Х		Х		Х	Х			
PET imaging and co-localising CT (subsequent subjects) ^{a, b}				←					>	•			
PK Blood Sampling for MS		Х		Х	Х	Х	Х	Х	Х	Х	Х	Х	Х
PK Blood Sampling for scintillation counting ^h		Х		x	х	х	х	Х	Х	Х	Х		
Bladder Void ^c		Х											
Urine Collection ^d				←				>					

2014N202021_00

CONFIDENTIAL

RES117169

Day of study	Day - 1	Day 1						Day 2	Day 4	Day 6	Day 13 ± 1 day	Day 20 ± 2 days	Day 31 ± 2 days
Time post dosing		Pre-dose	0	1 hour	3 hours	6 hours	8 hours	24 hours					
Adverse Event Review				←								`	
Concomitant Medication Review		←→										>	
Discharge								Х					
Outpatient Visit									Х	Х	Х	Х	Х
 a. Each PET/CT scan must be preceded b. For subsequent subjects (3rd and bey post injection. A maximum of 4 PET s c. Pre-dose urine will not be retained. d. 24 hour urine collection. Total volume stored for later MS PK analysis if reque e. Aliquot from 24 hr collection sample, t f. Triplicate measurement g. Prior to discharge 	yond) tim cans wil will be r uired. Ba	nings of PET I be conducte measured. Pa used on data	scans v ed in ea art of uri from firs	vill be base ch subject ine sample st 2 subjec	ed on data a	d for scintil	lation coun	ting. An aliqu	iot will be	utilized f	or UPCR assessme		

h. Aliquot from MS PK blood samplei. Urine sample to be collected prior to discharge i.

Note: all time points are relative to start of infusion administration.

CONFIDENTIAL

RES117169

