a. Each PET/CT scan must be preceded by heart rate and blood pressure assessments. b. For subsequent subjects (3rd and beyond) timings of PET scans will be based on data analysis from subjects 1 and 2 and may be carried out anytime between 1 and 10-12 days post injection. A maximum of 4 PET scans will be conducted in each subject. c. Pre-dose urine will not be retained. d. 24 hour urine collection. Total volume will be measured. Part of urine sample will be used for scintillation counting. An aliquot will be utilized for UPCR assessment and another stored for later MS PK analysis if required. Based on data from first 2 subjects, urine may be collected for longer than 24 hrs post dose for subsequent subjects. e. Aliquot from 24 hr collection sample, taken after 24 hr collection is complete. f. Triplicate measurement g. Prior to discharge h. Aliquot from MS PK blood sample							12 days iother						

i. Urine sample to be collected prior to discharge

Note: all time points are relative to start of infusion administration.

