10.3.3. Reporting Process & Standards

Reporting Process					
Software					
The currently sup	oported versions of SAS software SAS 9.4 will be used.				
Reporting Area					
HARP Server	: uk1salx00175				
HARP Area	: gsk3128349/res117169/final				
QC Spreadsheet	: gsk3128349/res117169/final/qc				
Analysis Datasets					
Analysis datasets will be created according to Legacy GSK A&R dataset standards					
Generation of RTF Files					
RTF files will be g	generated for all the tables				

Reporting Standards

General

- The current GSK Integrated Data Standards Library (IDSL) will be applied for reporting, unless otherwise stated:
 - 4.03 to 4.23: General Principles
 - 5.01 to 5.08: Principles Related to Data Listings
 - o 6.01 to 6.11: Principles Related to Summary Tables
 - 7.01 to 7.13: Principles Related to Graphics

Formats

- All data will be reported according to the actual treatment the subject received unless otherwise stated.
- GSK IDSL Statistical Principles (5.03 & 6.06.3) for decimal places (DP's) will be adopted for reporting of data based on the raw data collected.
- Numeric data will be reported at the precision collected on the eCRF.
- The reported precision from non eCRF sources will follow the IDSL statistical principles.

Planned and Actual Time

- Reporting for tables, figures and formal statistical analyses :
 - Planned time relative to dosing will be used in figures, summaries, statistical analyses and calculation of any derived parameters, unless otherwise stated.
 - The impact of any major deviation from the planned assessment times and/or scheduled visit days on the analyses and interpretation of the results will be assessed as appropriate.
- Reporting for Data Listings:
 - Planned and actual time relative to study drug dosing will be shown in listings (Refer to IDSL Statistical Principle 5.05.1).
 - Unscheduled or unplanned readings will be presented within the subject's listings.
 - Visits outside the protocol defined time-windows (i.e. recorded as protocol deviations) will be included in listings but omitted from figures, summaries and statistical analyses.

Reporting Standard	S					
Unscheduled Visits						
Unscheduled visi	ts will not be included in summary tables.					
Unscheduled visi	ts will not be included in figures.					
All unscheduled v	visits will be included in listings.					
Descriptive Summa	ry Statistics					
Continuous Data	Refer to IDSL Statistical Principle 6.06.1					
Categorical Data	N, n, frequency, %					

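### PET scans in Protocol Table 1 are timed from the end of the 20-minute infusion and in the Time and Events table from its start, and the SAP reports PET on planned time, which matters for the earliest scans

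*Protocol*

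**What the plan says.** **Scan clock in Table 1.** Protocol 4.1.2 introduces the scan times of subjects 1 and 2 with "Following completion of the IV infusion the subject will be scanned at the following times". Subject 1 is scanned at 1 h ± 30 min, 6 h ± 1 h, 24 h ± 1 h and Day 6. Subject 2 is scanned at 3 h ± 30 min, 8 h ± 1 h, Day 4 and Day 6.

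**Clock in the Time and Events table.** Protocol 7.1.2 puts the same scans in its 1, 3, 6, 8 and 24 hour columns, alongside the PK blood samples, and notes that "all time points are relative to start of infusion administration". SAP 10.2.1 repeats this: "Note: all time points are relative to start of infusion administration". Protocol 4.1 sends the reader to that table: "NOTE: Please refer to time and events table for PET and PK blood sampling timings".

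**Size of the gap.** Protocol Section 6 gives the dose as "IV as a continuous infusion over 20 mins".

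**Time used in analysis.** SAP 10.3.3 makes planned time relative to dosing the default for figures, summaries and derived parameters, without saying whether dosing means the start or the end of the infusion. SAP 8.1.3.1 overrides this for non-compartmental PK, which uses actual sampling times. SAP 7.1.2 has no such rule for PET, and the individual SUV figures in SAP 10.8.6 have planned time points on the x-axis.

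**The concern.** The primary objective is biodistribution over time, intended to inform a PBPK model. Tissue uptake and blood concentration are read together, so they need the same zero. As written, a PET value and a blood value that both carry the 1-hour label can be 20 minutes apart.

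Plasma falls slowly at these times, so the gap does little harm there. Extravascular uptake starts from zero and, in an averaged pool, is still rising nearly in proportion to time at 1 h, so 20 minutes is a sizeable share of what has accumulated. Among the first two subjects, one has the 1 h scan and the other has the 3 h scan. A fixed offset between clocks is a bias at those points and is not averaged out between the two subjects. Their data may also be used to set the scan times of later subjects.

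**Working it through.** The documents give no figure for the effect of this gap, so there is none to reproduce. The check derives one.

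**Inputs from the documents**
- Infusion duration T = 20 min = 1/3 h (Protocol Section 6).
- "Total extravascular albumin is about twice that of the intravascular pool" (Protocol 2.1), so plasma holds 1/3 of total albumin and the extravascular pool 2/3.
- Exchange r = 4–5% of total albumin per hour (Protocol 2.1).
- ⁸⁹Zr half-life 3.3 days (Protocol 4.1).

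**Assumptions**
- The tracer follows albumin.
- The extravascular space is one averaged pool.
- Elimination is ignored over these hours.

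**Rates.** The exchange figure is a share of total albumin, so it is converted to each pool:
- out of plasma: r ÷ (1/3) = 3r = 0.12–0.15 per h
- back to plasma: r ÷ (2/3) = 1.5r
- sum: L = 4.5r, which is 0.2025 per h at r = 4.5%

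**Extravascular share of dose** at time t from the start of infusion (t ≥ T):

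E(t) = (2/3) × [1 − (e^(−L(t−T)) − e^(−Lt)) / (LT)]

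**Worked example, nominal 1 h, r = 4.5%, LT = 0.0675**
- Start clock, t = 1 h: (2/3) × [1 − (0.8737 − 0.8167)/0.0675] = 10.3% of dose.
- End clock, t = 1 h 20 min: (2/3) × [1 − (0.8167 − 0.7634)/0.0675] = 14.0% of dose.
- Change: +3.7 points of dose; 14.02/10.34 − 1 = +36%.
- Plasma: 85.98/89.66 − 1 = −4.1%.

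**All early scans, start clock to end clock**

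| Nominal time | Change in extravascular share, r = 4.5% | Relative change, r = 4–5% |
|---|---|---|
| 1 h | +3.7 points (3.3 to 4.0 for r = 4–5%) | +35 to +36% |
| 3 h | +2.5 points | +8.1 to +8.8% |
| 6 h | +1.3 points | +2.7 to +3.1% |
| 8 h | +0.9 points | +1.5 to +1.9% |
| 24 h | +0.03 points | 0.1% or less |

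Label decay over the same interval is 1 − 2^(−(1/3)/(3.3 × 24)) = 0.29%, so decay correction does not drive the result.

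**Whole-region signal at 1 h.** A region's SUV includes its blood. If blood supplies a share f of the signal, the net ratio is f × 0.959 + (1 − f) × 1.356. The documents do not give f, so a range is assumed:
- f = 50%: about +16%
- f = 75%: about +6%
- f = 90%: about 0%

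**Fast-exchanging organs.** Protocol 2.1 says lungs, liver and kidney exchange rapidly but gives no rates. With a small organ pool driven by the plasma curve above (r = 4.5%) and equilibrating at an assumed 1 or 2 per h, the 1 h change in its extravascular signal is about +19% or +8%. At 3 h it is about −1.5% or −3.4%.

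**Table 1's own tolerance.** Moving the 1 h scan by ± 30 min on Table 1's clock takes the extravascular share from 14.0% down to 8.4% (−40%) or up to 19.1% (+36%).

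**The case against.** The strongest reply is that 20 minutes lies inside imprecision the plan already accepts. It is less than the ± 30 min and ± 1 h tolerances, and shorter than a scan: "Each PET scan will have a typical duration of up to 60 minutes". Table 1's hours bind only subjects 1 and 2, and only two of their eight scans (1 h and 3 h) are much affected. This stands as a limit on severity. It does not make the labelling harmless: planned-time reporting hides the tolerance error as well as the clock error, and actual elapsed time from one stated zero removes both.

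Three stronger readings are tempting, and the documents do not support them.

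- **That the primary endpoint is off by a third at 1 h.** The 35–36% applies to the extravascular amount in one averaged pool. The endpoint is SUV and activity in whole regions, which contain blood. At 1 h on the start clock about 90% of the dose is still in plasma, and in a blood-dominated region the net change may vanish.
- **That scans will be dropped because the clocks disagree.** The SAP says that visits outside protocol time windows "will be included in listings but omitted from figures, summaries and statistical analyses". For the hourly scans only Table 1 states a tolerance, on its own clock. The Time and Events table states none for its hour columns, so there is no second window for a scan to fall outside.
- **That the PBPK model will be fed mislabelled times.** Neither document says which time the PBPK input uses. Listings show planned and actual time, and the PET listing shell in SAP 10.9 has an actual-time field. The gap is that no single zero is stated and no rule tells the analyst to use actual time for PET.

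**Conclusion.** The point holds as a minor to moderate one. Table 1 and the Time and Events notes contradict each other by 20 minutes on when PET time starts, and the SAP gives the primary PET data a weaker time rule than it gives the PK parameters.

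The size depends on the quantity and the hour. It is material for early extravascular uptake at 1 h, modest at 3 h, small at 6–8 h and nil from 24 h on. Whole-region SUV at 1 h may change by anything from about zero to about 16% over the assumed 50–90% blood shares. These figures rest on the tracer behaving like albumin and on one averaged extravascular pool; fast-exchanging organs will differ. The contradiction itself rests on no assumption.

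**What to change.** 1. Reconcile Protocol Table 1 with the notes to the Time and Events table (Protocol 7.1.2, SAP 10.2.1) so that PET scans and blood samples share one stated zero time. The sponsor should choose which one; this review takes no position.
2. In SAP 10.3.3, define time relative to dosing by that same zero.
3. In SAP 7.1.2 and 10.3.3, add the PET counterpart of the PK rule: use actual elapsed scan time (from recorded scan start and stop) for PET time-course figures, any model of uptake over time and the PBPK input. Keep nominal time only to group the summary tables. Change the x-axis notes in SAP 10.8.6 to match.

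The cost is wording in two documents and one derived variable. No procedure, scan or sample is added.
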